#### 4.4. Indications, Contraindications and Warnings

##### 4.4.1 Indications

JuggerStitch™ Meniscal Repair Device is indicated for the repair of vertical longitudinal full thickness tears (e.g. bucket-handle) in the red-red and red-white zones. The device is not to be used for meniscal tears in the avascular zone of the meniscus.

##### 4.4.2 Contraindications

- (1) Infection.
- (2) Patients with mental or neurologic conditions who are unwilling or incapable of following postoperative care instructions.
- (3) Meniscal tears not suitable for repair because of the degree of damage (marked irregularity and complex tearing) to the meniscus body including degenerative, radial, horizontal cleavage and flap tears.

##### 4.4.3 Warnings

Biomet Sports Medicine internal fixation devices provide the surgeon with a means to aid in the management of meniscal tears. While these devices are generally successful in attaining these goals, they cannot be expected to replace normal healthy soft tissue or withstand the stress placed upon the device by full or partial weight bearing or load bearing, particularly in the presence of incomplete healing. Therefore, it is important that immobilization (use of external support, walking aids, braces, etc.) of the treatment site be maintained until healing has occurred. Surgical implants are subject to repeated stresses in use, which can result in fracture or damage to the implant. Factors such as the patient's weight, activity level, and adherence to weight bearing or load bearing instructions have an effect on the implant. The surgeon must be thoroughly knowledgeable not only in the medical and surgical aspects of the implant, but also must be aware of the mechanical and polymeric aspects of the surgical implants and the surgical technique.

- (1) Correct selection of the implant is extremely important. The potential for success in soft tissue fixation is increased by the selection of the proper type of implant. While proper selection can help minimize risks, the device is not designed to withstand the unsupported stress of full weight bearing, load bearing or excessive activity.
- (2) The implants can loosen or be damaged when subjected to increased loading associated with inadequate healing. If healing is delayed, or does not occur, the implant or the procedure may fail. Loads produced by weight bearing and activity levels may dictate the longevity of the implant.
- (3) Inadequate fixation at the time of surgery can increase the risk of loosening and migration of the device or tissue supported by the device.
- (4) Care is to be taken to assure adequate fixation of the meniscal tissue at the time of surgery. Failure to achieve adequate fixation through improper positioning or placement of the device can contribute to a subsequent undesirable result.
- (5) The use of appropriate immobilization and postoperative management is indicated as part of treatment until healing has occurred.
- (6) Correct handling of suture is extremely important. Avoid crushing or crimping damage due to application of surgical instruments such as forceps or needle holders.
- (7) DO NOT USE if there is loss of sterility of the device.
- (8) DO NOT USE opened or damaged devices. Use only devices that are packaged in unopened and undamaged containers. Do not use excessive force when inserting the device. Excessive force may cause damage to the device and/or adversely affect its performance.
- (9) Adequately instruct the patient. Postoperative care is important. The patient's ability and willingness to follow instructions is one of the most important aspects of successful soft tissue management.

- Patients affected with senility, mental illness, alcoholism, and drug abuse may be at a higher risk of device or procedure failure. These patients may ignore instructions and activity restrictions.
  - The patient is to be instructed in the use of external supports, walking aids, and braces that are intended to immobilize the repair site and limit weight bearing or load bearing.
  - The patient is to be made fully aware and warned that the device does not replace normal healthy tissue, and that the device can break, or be damaged as a result of stress, activity, load bearing, or weight bearing.
  - The patient is to be made aware and warned in advance of general surgical risks, possible adverse effects, and to follow the instructions of the treating physician.
  - The patient is to be advised of the need for regular postoperative follow-up examination as long as the device remains implanted. Noncompliance with postoperative instructions could lead to failure of the device, which could require additional surgery and device removal.
- (10) Do not reuse implants. While an implant may appear undamaged, previous stress may have created imperfections that would reduce the service life of the implant. Do not treat with implants that have been, even momentarily, placed in a different patient.
- (11) Device is single use only. After use, the device may be a potential biohazard. Reuse of devices labeled for single-use may result in product contamination, patient infection and/or failure of the device to perform as intended.
- (12) Patient smoking may result in delayed healing, non-healing and/or compromised stability in or around the placement site.

## 5. Objective and Content of Clinical Trial

### 5.1 Objective

The clinical safety and efficacy of the JuggerStitch™ in repair of meniscal tears are assessed by comparing the clinical data of the Fast-Fix 360.

### 5.2 Content

This trial was a prospective, multicenter, randomized controlled clinical trial to evaluate the clinical safety and efficacy of JuggerStitch™ all-suture meniscus suture system for arthroscopic repair of meniscus tears.

#### 5.2.1 Primary Endpoints

Lysholm Knee Score at postoperative 6 months.

#### 5.2.1 Secondary Endpoints

- (1) Immediate device success rate postoperatively;
- (2) Lysholm Knee Score at postoperative 3 months and 12 months;
- (3) Tegner Activity Score at postoperative 3 months, 6 months and 12 months;
- (4) Visual analogue scale (VAS) score for pain at postoperative 3 months, 6 months and 12 months;
- (5) Meniscus healing evaluated by Magnetic Resonance Imaging (MRI) scans at postoperative 6 months and 12 months;
- (6) Device-related adverse event rate.

### 6.1.3 Measures to reduce and avoid bias

- (1) The investigators participating in this study will receive training on the clinical trial protocol and the operating procedure for the investigational medical device, and strictly abide by the inclusion and exclusion criteria.
- (2) The sponsor will assign a qualified clinical trial monitor to monitor the study center, make quality control and monitoring records, and communicate with the investigators in time about the problems found during the monitoring.
- (3) Interventions will be performed on the subjects according to the randomization results obtained by the central randomization system.
- (4) Multi-center clinical study design is adopted to make the results more objective and reliable, and avoid data bias in single-center clinical study.
- (5) The subjects with good protocol compliance will be included as far as possible, and the subject's follow-up, withdrawal and dropout will be controlled during the clinical study period.
- (6) Fixed efficacy assessors will be arranged before and after treatment, who will receive training on strict efficacy assessment criteria to prevent detection bias.
- (7) To reduce data loss, data analysis will also be performed on subjects who withdraw from treatment.

### 6.1.4 Diagnosis and treatment method of the investigational medical device

- (1) Anesthesia and position: After the subject is under epidural or lumbar anesthesia, take a supine position according to the investigator's habitual surgical operation procedures, and take on a routine tourniquet to the roof of the index knee joint.
- (2) Surgical incision: Operate according to the standard operating procedure of arthroscopic surgery, and choose the subpatellar and medial lateral approach to the knee joint.
- (3) Exploration: Explore from the suprapatellar bursa, patellofemoral joint, medial compartment, medial malleolus fossa, lateral compartment, posterior medial compartment to posterior lateral compartment, conduct preoperative physical examination and MRI to assess the location of the meniscus tear and determine the repairability of the injury.

- (4) The investigator will then recheck whether the subjects meet the eligibility criteria, subjects who does not meet all inclusion criteria or meet any of the exclusion criteria will be deemed to screening failure under arthroscopy.
- (5) Surgical procedures: during the treatment of meniscus injury, for the combined articular loose body, the loose body should be removed and clean the joint. According to the injury location of meniscus, the probe will be used to determine and select the appropriate meniscal repair system.

### The Surgical Techniques for JuggerStitch™:

#### Step 1: Diagnostic Arthroscopy

[figure not shown]
Figure 1

Assess the location of the meniscal tear and determine the reparability of the lesion. Determine optimum medial portal placement using an 18-gauge spinal needle and direct arthroscopic visualization to create a medial working portal. Appropriate position is achieved when the needle enters just above the anterior medial meniscus parallel to the tibial joint surface (Figure 1).

Avoid placing the portal too superior or inferior and ensure the medial portal is large enough to readily pass the inserter and suture cutter.

[figure not shown]
For mid-body tears of the medial meniscus, the scope should be switched to the medial portal, and the lateral portal should be assessed by inserting the half pipe into the lateral portal. Should the half pipe not enter the joint just above the anterior lateral meniscus parallel to the tibial surface, the lateral portal should be expanded or a new lateral portal should be created.

#### Step 2: Decide on Proper Approach

[figure not shown]
Both straight and curved needle options are available to optimize implant positioning for repair. Utilize a probe through the medial portal to help determine whether a straight or curved needle is optimal. Posterior horn tears, whether medial or lateral, should be approached from the medial portal (Figure 2a). Approach the mid-body tears from the contralateral portal (Figure 2b). If the needle depth needs to be adjusted, push down on the white depth control slider in a forward motion to decrease the needle length exposed (Figure 3).

#### Step 3: Position the JuggerStitch™ Meniscal Repair Device

[figure not shown]
pointed inferiorly when penetrating the surface of the meniscus. Once penetrated, rotate the inserter 180 degrees and advance the needle until the clear depth limiting tube contacts the surface of the meniscus

#### Step 4: Deploy the First Anchor

Once the JuggerStitch™ depth limiter is in contact with the anterior surface of the meniscus, use two hands, one to hold the handle while the other advances the black button (Figure 7). Fully advance the black button to deploy the first anchor. (Figures 8a and 8b). Fully retract the black button and subsequently pull the needle tip gently out of the meniscus (Figure 9a and 9b).

#### Step 5: Deploy the Second Anchor

Reposition the needle tip at the desired location and advance the needle tip as described previously (Figure 10). Once the depth gage contacts the surface of the meniscus, advance the black button forward to deploy the second anchor (Figure 11). Fully retract the black button and then completely remove the meniscal inserter from the joint (Figure 12).

**Pearl:** Always work towards the scope. Insert the first anchor away from the scope lens of view and insert the second anchor closer to the lens and field of view.

**Pearl:** Do not remove the device from the joint between anchors as this could create a tissue bridge.

[figure not shown]

Figure 13a

Figure 13b

Figure 14

### Step 6: Vertical Mattress Technique

Insert the first anchor on the inferior meniscal rim. Then, insert the second anchor superior to the tear on the meniscal rim. Anchors placed in the superior meniscus may require less deployment depth compared to anchors placed in the inferior meniscus because the superior meniscus is typically less thick than the inferior meniscus (Figure 13).

To lessen the needle depth for the superior position, push down on the white depth control slider in a forward motion to decrease the depth of the needle until desired measurement is reached (Figure 14).

### Step 7: Tension the Suture

After retracting the JuggerStitch™ from the joint, a suture loop and a single strand will remain protruding from the portal.

[figure not shown]

Figure 15

Figure 16

Pull the blue/white side of the loop with multiple short tugs using the index and middle finger to set the anchors at the repair site (Figures 15 & 15a). The anchor is fully set once the blue/white portion of the suture loop no longer moves. Confirm under visualization of the scope at the repair site (Figure 15b).

Next, pull the white single strand to reduce the large loop down to the surface of the meniscus. Pull on the strand until tension on the second loop matches the tension of the first loop (Figure 16 & 16a). At this time, if desired, a probe may be utilized to check the repair site for

### Step 8: Cut the Suture

Place JuggerStitch™ 2-0 MaxBraid™ suture through kite (Figures 17 & 17a).

[figure not shown]

Figure 17

Figure 17a

Once suture is through kite, use white pull tab to pull suture through the eyelet of the suture cutter (Figure 18). Please note that when reloading suture through the suture cutter to always load suture in this direction.

appropriate tension.

## Surgical Technique for Fast-Fix 360:

### Step 1: Determine the Depth of Pin

Use the meniscus depth probe to determine the desired depth. Place the tip of the probe at the meniscus-synovial junction and determine the width of the meniscus at the desired delivery needle entry point. For average sized knees, a depth of 14mm is usually sufficient, and this length can be adjusted either externally or internally on the probe. The laser marks on the tips also serve as a reference. As shown in figure 19.

Figure 19 Fast-Fix 360 Probe

### Step 2: Insertion of suture needle

Insert Fast-Fix360 needle into the joint through the appropriate arthroscopic approach. Easy insertion by using slotted casing. As shown in figure 20.

Figure 20 Needle Insertion

### Step 3: Deploy the First Anchor

Place the first anchor (T1) on the capsular side of the tear. Insert the FastFix360 needle into the capsule or tear any remaining meniscus tissue on the side of the capsule. Keep the conveying needle in the appropriate position and push the expansion slider forward to expand T1; The correct deployment of the implant is accompanied by a clicking sound. For better suture management and to prevent removal of the second implant (T2), release the unfurl slider and slowly pull the needle out of the meniscus, keeping the needle within the grossed socket and the arthroscopic field of view. As shown in figure 21-23.

Figure 21 Insert Needle into the Meniscus Tissue

[figure not shown]

Figure 22 Deploy the first implant T1

[figure not shown]

Figure 23 Unfold the first Anchor T1

#### Step 4: Deploy the Second Anchor T2

Place the slotted casing on the internal meniscus fragment at the desired entry point (if required). The entry point of the second (T2) anchor should be at least 5mm away from the tear. Propel the insertion of needle until the depth of penetration limiter touches the meniscus surface (Figure 24). With the needle

insertion in place, push the unroll slider forward to deploy T2. As with T1, proper deployment of T2 is accompanied by a "click" sound. After the T2 is deployed, slowly remove the conveying needle from the connector. Tighten the thread to make the knot tight. Slide the pusher/suture cutter onto the knot to cut off excess stitches and complete the suture. As shown in figure 24-26.

[figure not shown]

Figure 24 Deploy the Second Anchor T2

[figure not shown]

Figure 25 Unfold the Second Anchor T2

Figure 26 Tension the Suture

The fixed position of the anchors and the number of devices used are determined according to the type of injury, and the details of the use of the anchors and the repair of combined injuries are recorded.

Probe to confirm that the meniscus is well fixed, the soft anchor and suture are stable, rinse the incision, check the instrument dressing is correct, suture the incision, bandage.

### **6.1.5 Selection of subjects**

#### **6.1.5.1 Inclusion criteria of subjects**

- (1) 18~60 years old (18 and 60 inclusive);
- (2) Patient who are scheduled for meniscal repair with a vertical longitudinal full-thickness tears (e.g. bucket-handle) in the red-red and red-white zones;
- (3) Patients who can understand all risks and benefits described in the informed consent form (ICF), and are willing to comply with the guidance for rehabilitation, and the follow-up visits specified in the clinical trial protocol, and voluntarily participate in the trial and sign the ICF;

#### **6.1.5.2 Exclusion criteria of subjects**

- (1) Patient has meniscal tears in the avascular zone of meniscus;
- (2) Meniscal tears not suitable for repair because of the degree of damage (marked irregularity and complex tearing) to the meniscus body including degenerative, radial, horizontal cleavage, flap and root tears;
- (3) Patient with multiple ligament injuries of the affected knee joint;
- (4) Patient with adhesion of the affected knee joint;
- (5) Patient is planned to accept intraoperative or postoperative intra - articular injection is planned;
- (6) Articular surface cartilage injury of the targeted knee assessed by the International Cartilage Repair Society (ICRs) is grade 3-4;
- (7) Kellgren-Lawrence grades of documented radiographic evidence of osteoarthritis (OA) in the affected knee is  $\geq III$ .
- (8) Instability or valgus/varus deformity( $>50$ ) of the affected knee;
- (9) Patient has acute or chronic, local or systemic infections;
- (10) Patient with metabolic diseases;
- (11) Abnormal liver and kidney function (Creatinine 3 times higher than the upper limit of normal value or alanine aminotransferase or aspartate aminotransferase 3 times higher than the upper limit of normal value) before operation;
- (12) History of operation in the affected knee;
- (13) Acute myocardial infarction or stroke occurred within 6 months before operation;
- (14) Patients are known allergy to any material (polyethylene, polypropylene, polyester, polyetheretherketone) of the implants;
- (15) Patient is pregnant or known to be pregnant;
- (16) Other circumstances that the researchers believe that may affect the efficacy and safety evaluation of the investigated medical devices;
- (17) Patients are currently participating in other clinical trials.

#### **6.1.5.3 Criteria and procedure for suspending the trial/treatment**

The clinical trial suspension means that the clinical trial does not end according to the protocol, but all trials are stopped midway. The purpose of terminating the clinical trial is to protect the rights and interests of the subjects and ensure the quality of the clinical trial. Except for Item 5 below, the Sponsor and the Investigator shall jointly negotiate whether to terminate the study:

- (1) If serious safety problems occur during the clinical trial, the clinical trial should be terminated in time;
- (2) If the product is found to be of no clinical value during the clinical trial, the clinical trial should be terminated;
- (3) It is difficult to evaluate the effect of the product because there is a major error in the clinical study scheme in the process of clinical trial; Or the program in the implementation of serious deviation, continue, it is difficult to evaluate the effect of the product should be terminated clinical trial;
- (4) The Sponsor requests termination (for financial reasons, etc.)
- (5) The National Medical Products Administration (NMPA) ordered the termination of the clinical trial for some reason.

After the termination of the study, the investigator shall continue to provide appropriate treatment to the subjects from the perspective of protecting their rights and interests, and shall inform the subjects in detail of the treatment and treatment they have received during the study period. Subjects' data can still be used to evaluate product safety.

#### **6.1.5.4 Enrollment duration**

The first subject is scheduled to be enrolled in December 2021, and the total enrollment time limit is set to 6 months.

#### **6.1.5.5 Expected overall duration of the clinical trial and the rationale**

The expected overall duration of the clinical trial is 18 months, calculated from the first subject enrolled in the group. The recruitment time is set to 6 months, and the postoperative follow-up time is 12 months.

#### **6.1.5.6 Expected duration of each subject's participation**

The patients will be hospitalized for 2-5 days, and followed up for 12 months after discharge.

#### **6.1.5.7 Number of subjects required for the clinical trial**

47 patients will be included in the investigational group and the control group, respectively. A total of 94 subjects will be included in this clinical trial.

#### **6.1.6 Efficacy evaluation approach**

##### **6.1.6.1 Description of efficacy parameters**

Primary evaluation: Difference of Lysholm Knee Score from baseline to postoperative 6 months;

Secondary evaluation: Significant improvement in follow-up Tegner Activity Score and VAS Score for pain compared with the preoperative ones, is used as the basis for evaluating the efficacy of the investigational medical device.

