## **7. Statistics Considerations**

## 7.1 Statistical hypothesis testing, statistical method selection and statistical analysis

### 7.1.1 Statistical hypothesis testing

This trial is intended to adopt a prospective, multi-center, randomized controlled design, and its comparison type is a non-inferiority trial. The primary evaluation indicator is set as the difference of Lysholm Knee Score for knee function at 6 months postoperatively.

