### 7.1.2 Statistical analysis method

SAS® 9.40 statistical software is used for statistical analysis.

Two-sided tests are used in all statistical tests (unless otherwise specified), and a *P* value of less than 0.05 will be considered as statistically significant.

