#### Primary Efficacy analysis:

The efficacy indicators will be analyzed by PPS and FAS.

Statistical analysis of the primary endpoint:

$H_0: \pi_1 - \pi_2 \leq -\Delta$ ;

$H_1: \pi_1 - \pi_2 > -\Delta$

The difference of Lysholm Knee Score at postoperative 6 months from baseline will be compared between the two groups using covariance analysis model, and the modified LS means and 95% confidence interval (CI) of the difference between the two groups at postoperative 6 months from baseline will be estimated. If the lower limit of 95% confidence interval is greater than the non-inferiority margin, the research hypothesis will be established. To investigate the consistency among centers, a covariance analysis model containing interaction terms between centers and groups will be considered on the basis of the above covariance analysis model, and the significance of interaction terms will be judged at the level of 0.10.

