#### Secondary Efficacy analysis:

The secondary efficacy indicators will be analyzed by PPS and FAS.

Statistical description and inference of data will select suitable descriptive indicators and hypothesis testing methods according to the characteristics of data.

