## 7.2 Calculation of sample size

### 7.2.1 Total sample size

The clinical trial hypothesis is based on several publications [22-26], the difference between Lysholm Knee Score at baseline and postoperative 6 months was 30. It is assumed that the difference between Lysholm Knee Score at baseline and postoperative 6 months after arthroscopic meniscus repair will be 34 for both the experimental group and the control group, the standard deviation is set to 8.00, and the non-inferiority margin is set to 5.1 under 15% of the difference, and the test level  $\alpha$  is set to one-sided 0.025 and  $\beta$  to 0.2. Based on the above assumptions, the sample size of each group is 40. Considering that the clinical dropout rate in the clinical trial process was 15%, it was recommended to include 94 subjects in this trial. The calculation formula and required parameters for sample size are as follows:

$$n_T = n_C = \frac{2(Z_{1-\alpha/2} + Z_{1-\beta})^2 \sigma^2}{(|D| - \Delta)^2}$$

where,  $\alpha$ = Expected standard deviation of control group;  $|D|$ = Pooled variance of the test group and the control group,  $\Delta$ = Non-inferiority test margin.

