### 7.3 Level of Significance and Power

The statistical test level  $\alpha$  is set to one-sided 0.025, and the power of test  $1-\beta$  is set to 80%.

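### Section 6.1.6.1 judges Tegner and VAS by significant improvement over the preoperative score, not against Fast-Fix 360, so these two secondary results cannot show relative efficacy

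*Combined protocol and SAP*

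**What the plan says.** Section 6.1.6.1 (Description of efficacy parameters) sets out how the device's efficacy is judged on secondary measures in one sentence, which reads in part: "Significant improvement in follow-up Tegner Activity Score and VAS Score for pain compared with the preoperative ones, is used as the basis for evaluating". It names neither the control arm, nor a margin, nor a test.

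The rest of the plan is comparative. Under section 5.1, safety and efficacy "are assessed by comparing the clinical data of the Fast-Fix 360". Section 7.1.1 says of the design that "its comparison type is a non-inferiority trial". In the primary efficacy part of 7.1.2, the change in Lysholm score at 6 months "will be compared between the two groups using covariance analysis model".

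For secondary endpoints, 7.1.2 says only: "Statistical description and inference of data will select suitable descriptive indicators and hypothesis testing methods according to the characteristics of data". Tests are two-sided at 0.05 unless stated otherwise. Section 6.1.6.2 and the flow chart in 6.2.1 schedule Tegner and VAS before surgery and at 3, 6 and 12 months for all subjects. Section 7.5 makes trial success depend on the between-group Lysholm comparison alone.

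**The concern.** Patients enter with a tear that needs repair, and both arms receive an arthroscopic repair followed by the same rehabilitation. A score that improves after surgery reflects the repair itself, rehabilitation, natural recovery and regression to the mean, as well as the particular device. The randomised control arm is there to remove everything except the device. A criterion that looks only at change from the preoperative score does not use it.

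The protocol's own background (section 4.2) illustrates this. It describes a retrospective comparison of Fast-Fix 360 with another suture in which function improved significantly in both groups, and then separately reports that functional scores did not differ between them. Only the second statement compares treatments.

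At stake is the meaning of the Tegner and VAS efficacy claims. A report that follows 6.1.6.1 could describe the device as effective on both instruments when the result says little about its performance relative to Fast-Fix 360.

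**Working it through.** **1. The plan's own figure.** Section 7.2.1 assumes that the Lysholm change "will be 34 for both the experimental group and the control group", with SD 8.00, margin 5.1, one-sided alpha 0.025 and 80% power. The normal approximation gives n = 2 × (1.960 + 0.842)² × 8² / 5.1² = 38.6, so 39 per group. The t-based calculation gives 40 (power 80.4%; 79.4% at 39). The stated 40 is reproduced. With 15% dropout, 40 / 0.85 = 47.06, taken as 47 per group and 94 in total. I therefore use 40 evaluable patients per arm. No sample-size figure is stated for Tegner or VAS.

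**2. Threshold of the before-after rule.** The test is not named. I take a paired t test in one arm, two-sided 0.05. It is significant in the favourable direction when observed mean gain / SD of change exceeds t(0.975, 39) / √40 = 2.023 / 6.325 = 0.32. With 47 patients the threshold is 0.29 SD; with 37 (about 20% dropout, the limit in section 7.4) it is 0.33 SD.

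**3. Chance that a half-effect device passes.** Let the control's true gain be d SD and the test device's gain d/2. The pass probability is P(T > 2.023), where T is noncentral t with 39 df and noncentrality (d/2) × √40. The last column is the power of a two-sided 0.05 two-sample t test, 40 per arm, to detect the same deficit. The values of d are assumptions.

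| Control gain (SD) | Device gain (SD) | Noncentrality | Passes before-after rule | Between-arm test detects deficit |
|---|---|---|---|---|
| 0.8 | 0.4 | 2.53 | 69% | 42% |
| 1.0 | 0.5 | 3.16 | 87% | 60% |
| 1.5 | 0.75 | 4.74 | 99.6% | 91% |
| 2.0 | 1.0 | 6.32 | >99.9% | 99% |

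As the control benefit grows, half of it becomes a larger deficit. The before-after rule then passes the device more often, while the between-arm test detects the deficit more often.

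**4. Precision of the alternative.** The unadjusted 95% CI half-width for the between-arm difference at 40 per arm is 1.991 × √(2/40) = 0.45 SD. Both the table and this half-width assume roughly normal changes with equal SDs. For Tegner, an ordinal scale from 0 to 10, that is an approximation.

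**The case against.** The strongest reply is that 6.1.6.1 describes parameters and is not the analysis plan. The line just above defines the primary measure as a change from baseline, also without mentioning the control, yet 7.1.2 analyses it between groups. On this view the secondary sentence is loosely worded, 7.1.2 governs, and its open text admits a between-arm test.

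Part of this stands. The open text does permit a between-arm analysis, so a reader who infers that the plan discards the control arm for these endpoints goes too far. But the two lines are not alike. The primary line defines a measure. The secondary line says what counts as evidence of efficacy, and the comparator it names is the preoperative score. For the primary endpoint, 7.1.2 supplies the between-group contrast. For Tegner and VAS, no section does, so 6.1.6.1 remains the only stated criterion.

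A second reply is that improvement is not guaranteed. Tegner grades work and sport, and Appendix 9 restricts squatting for 3 months and sudden stops or turns for 6 months. Early Tegner gains may therefore be small, and high pass rates are more plausible for VAS and at 12 months. This stands, and it is why a range is shown. It does not rescue the rule: if shared restrictions can make a good device fail it, the rule still measures recovery and not relative performance.

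**Conclusion.** The point holds for two instruments. Section 6.1.6.1 sets a criterion for Tegner and VAS that does not answer the comparative question in 5.1, and 7.1.2 does not replace it. For control gains of 0.8 to 2.0 SD, a device with half the control's benefit would meet the criterion about 69% to more than 99.9% of the time. This rests on 40 evaluable patients, a within-arm paired test (the natural reading, but not named in the text) and assumed gains in SD units.

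Three stronger conclusions are tempting, and the documents support none of them:

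- **That an inferior device could pass the trial.** Section 7.5 rests success on the between-group Lysholm test, and no secondary endpoint has a pass/fail role.
- **That all secondary efficacy is judged before-after.** The sentence covers Tegner and VAS only. Device success, Lysholm at 3 and 12 months, MRI healing and device-related adverse events have no such rule.
- **That a pass is nearly certain whatever the device does.** This depends on gains the documents do not give. The Lysholm assumption (34 points, SD 8, more than 4 SD) belongs to another instrument and cannot be carried over.

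The rule should be corrected, but the primary conclusion does not depend on it.

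**What to change.** Replace the secondary sentence in 6.1.6.1 and cross-refer to it in the secondary efficacy part of 7.1.2. For Tegner and VAS at 3, 6 and 12 months, specify the between-arm difference in change from baseline, adjusted for the baseline score, with a 95% CI. Adjustment for centre, and a rank-based or ordinal method for Tegner, are reasonable options but not essential. Keep within-arm change as description only, not as a basis for an efficacy claim.

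No margin is stated for either instrument. The intervals should therefore be presented as estimates, and a non-significant difference should not be read as equivalence.

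The cost is wording. Both arms already provide the scores at every visit, and section 7.8 allows the analysis plan to be revised before it is finalised ahead of database lock; the 6.1.6.1 wording needs a protocol amendment under 14.2. The drawback is that between-arm results will look less favourable than before-after p-values, and with a half-width near 0.45 SD before baseline adjustment they may be inconclusive.
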